### 11.2.6 Criteria for Molecular CR and Minimal Residual Disease (MRD) measurement

We will measure MRD in patients who achieve CR to determine the number of patients who are MRD negative vs MRD positive.

#### 11.2.6.1 MRD by LymphoSIGHT

MRD will be carried out according to the LymphoSIGHT™ method (Sequanta, Inc., San Francisco, CA). Prior studies have compared this technique to the traditional MRD immunofluorescence technique, as previously reported  and showed that MRD by LymphoSIGHT is a sensitive method that can be used in future clinical practice.

For MM diagnostic samples, genomic DNA will be amplified using locus-specific primer sets for the immunoglobulin heavy-chain locus (IGH) complete (IGH-VDJH), IGH incomplete (IGH-DJH), and immunoglobulin κ locus (IGK). The amplified product will be subjected to

CONFIDENTIAL

This document is confidential. Do not disclose or use except as authorized.

sequencing, and the sequences and frequencies of the different clonotypes in the sample will be obtained. Myeloma gene rearrangements will be identified. Patients in whom a high-frequency myeloma clone (>5%) is not identified will be excluded from the MRD analysis. MRD will be assessed in patients with a high-frequency myeloma clone using the IGH-VDJH and IGK or IGH-VDJH, IGH-DJH, and IGK assays. Once the absolute amount of total cancer-derived molecules present in a sample will be determined, a final MRD measurement will be calculated, providing the number of cancer-derived molecules per 1 million cell equivalents. In cases in which 2 or more tumor clones existed, the clone with the highest MRD value will be reported. Molecular CR will be defined according to the International Myeloma Working Group (IMWG) consensus recommendations.

#### 11.2.6.2 Modified EBMT Response Criteria

Response	Criteria for Response a
Complete response (CR)	Requires all of the following:  Disappearance of the original monoclonal protein from the blood and urine on at least two determinations for a minimum of six weeks by immunofixation studies.  <5% plasma cells in the bone marrow on at least two determinations for a minimum of six weeks. b  No increase in the size or number of lytic bone lesions (development of a compression fracture does not exclude response). c  Disappearance of soft tissue plasmacytomas for at least six weeks.
Near Complete Response (nCR)	Requires the following:  Same as CR, but immunofixation studies continue to show presence of the monoclonal protein
Very Good Partial Response (VGPR)	Requires the following: $\geq 90\%$ reduction in serum M-protein plus urine M-protein level <100mg per 24 hours on at least two determinations for a minimum of six weeks.

CONFIDENTIAL

This document is confidential. Do not disclose or use except as authorized.

Partial response (PR)	
PR includes participants in whom some, but not all, criteria for CR are fulfilled providing the remaining criteria satisfy the requirements for PR. Required all of the following:
 
≥50% reduction in the level of serum monoclonal protein for at least two determinations six weeks apart.
 
If present, reduction in 24-hour urinary light chain excretion by either ≥90% or to <200 mg for at least two determinations six weeks apart.
 
≥50% reduction in the size of soft tissue plasmacytomas (by clinical or radiographic examination) for at least six weeks.
 
No increase in size or number of lytic bone lesions (development of compression fracture does not exclude response).c

Minimal response (MR)	
MR included participants in whom some, but not all, criteria for PR were fulfilled, providing the remaining criteria satisfied the requirements for MR. Required all of the following:
 
≥25% to ≤ 49% reduction in the level of serum monoclonal protein for at least two determinations six weeks apart.
 
If present, a 50 to 89% reduction in 24-hour light chain excretion, which still exceeds 200 mg/24 h, for at least two determinations six weeks apart.
 
25-49% reduction in the size of plasmacytomas (by clinical or radiographic examination) for at least six weeks.
 
No increase in size or number of lytic bone lesions (development of compression fracture does not exclude response).c

No change (NC)	Not meeting the criteria for MR or PD.

CONFIDENTIAL

This document is confidential. Do not disclose or use except as authorized.

Response	Criteria for Response a
Progressive disease (PD) (for participants not in CR)	
Requires one or more of the following:
 
>25% increased in the level of serum monoclonal paraprotein, which must also be an absolute increase of at least 5 g/L and confirmed on a repeat investigation.
 
>25% increased in 24-hour urinary light chain excretion, which must also be an absolute increase of at least 200 mg/24 h and confirmed on a repeat investigation.
 
>25% increased in plasma cells in a bone marrow aspirate or on trephine biopsy, which must also be an absolute increase of at least 10%.
 
Definite increase in the size of existing lytic bone lesions or soft tissue plasmacytomas.
 
Development of new bone lesions or soft tissue plasmacytomas (not including compression fracture).
 
Development of hypercalcemia (corrected serum calcium >11.5 mg/dL or 2.8 mmol/L not attributable to any other cause).

CONFIDENTIAL

This document is confidential. Do not disclose or use except as authorized.

Relapse from CR	
Required at least one of the following:
 
Reappearance of serum or urinary paraprotein on immunofixation or routine electrophoresis confirmed by at least one follow-up and excluding oligoclonal immune reconstitution.
 
<math>\geq 5\%</math> plasma cells in the bone marrow aspirate or biopsy.
 
Development of new lytic bone lesions or soft tissue plasmacytomas or definite increase in the size of residual bone lesions (not including compression fracture).
 
Development of hypercalcemia (corrected serum calcium <math>>11.5</math> mg/dL or 2.8 mmol/L not attributable to any other cause).e

-----------------	--

- a Based on the criteria reported by Blade *et al.*, 1998.
- b Per Blade *et al.*, 1998, if absence of the monoclonal protein is sustained for 6 weeks it is not necessary to repeat the bone marrow except in participants with nonsecretory myeloma where the marrow examination must be repeated after an interval of at least 6 weeks to confirm CR.
- c Per Blade *et al.*, 1998, skeletal X-Rays are not required for the definition of response, but if performed there must be no evidence of progression of bone disease (no increase in size or number of lytic bone lesions).
- d It is suggested that the reference point for calculating any increase should be the lowest value of the preceding confirmed response (MR, PR or CR) or the baseline value if there is no previous confirmed response.
- e Other clinical data may be requested by the IRC, as necessary, to assess the cause of the hypercalcemia.

#### 11.2.8 Progression-Free Survival

Progression-Free Survival (PFS): the primary endpoint in this study. PFS is defined as the time from randomization to the disease progression or death from any cause. Patients who have not

CONFIDENTIAL

This document is confidential. Do not disclose or use except as authorized.

progressed or died are censored at the date last known progression-free.

#### 11.2.9 Response Review

Central review of disease response assessments is not planned.

### **12. DATA REPORTING / REGULATORY REQUIREMENTS**

Adverse event lists, guidelines, and instructions for AE reporting can be found in Section 7.0 (Adverse Events: List and Reporting Requirements).

#### **12.1 Data Reporting**

##### 12.1.1 Method

The QACT will collect, manage, and perform quality checks on the data for this study.

##### 12.1.2 Responsibility for Data Submission

Investigative sites within DF/HCC or DF/PCC are responsible for submitting data and/or data forms to the QACT according to the schedule set by the QACT. Data should be entered within 14 business days of the corresponding visit and within 14 business days of the end of a cycle for any forms to be completed per cycle.

#### **12.2 Data Safety Monitoring**

The DF/HCC Data and Safety Monitoring Committee (DSMC) will review and monitor toxicity and accrual data from this study. The committee is composed of clinical specialists with experience in oncology and who have no direct relationship with the study. Information that raises any questions about participant safety will be addressed with the Overall PI and study team.

The DSMC will review each protocol up to four times a year or more often if required to review toxicity and accrual data. Information to be provided to the committee may include: up-to-date participant accrual; current dose level information; DLT information; all grade 2 or higher unexpected adverse events that have been reported; summary of all deaths occurring with 30 days of intervention for Phase I or II protocols; for gene therapy protocols, summary of all deaths while being treated and during active follow-up; any response information; audit results, and a summary provided by the study team. Other information (e.g. scans, laboratory values) will be provided upon request.

### **13. STATISTICAL CONSIDERATIONS**

#### **13.1 Study Design/Endpoints**

The primary endpoint of this phase II study is to determine the proportion of high risk

CONFIDENTIAL

This document is confidential. Do not disclose or use except as authorized.

smoldering multiple myeloma (SMM) patients who are progressive free at 2 years after receiving treatment (Elotuzumab + lenalidomide+ Dexamethasone). The secondary objectives include toxicities, objective response rate, time to progression, duration of response, and overall survival. In addition, we will examine the molecular evolution of the tumor cells, the role of circulating tumor cells and immune cells, and the role of NK cells and other immune cells present in the bone marrow in the progression of smoldering MM.

The proportion of patients who achieve progression free at 2 years will be compared to the rate published for the high risk SMM. By the Mayo Clinic model for risk factors, the median time to progression for patients with high risk SMM was only 1.9 years. Therefore, we assume that for this study, a 2-years progression-free rate of 50% will not be considered promising and a true progression free rate of 70% or higher will be considered promising. A single-stage design will be employed with 39 eligible patients entered. If 24 or more of the 39 eligible patients are progression free at 2 years (observed rate of 62%), we will conclude that this treatment warrants further study. The probability of concluding that the treatment is effective if the true rate is 50% is 0.10 and is >0.9 if the true rate is 70%. Assuming an ineligibility rate of 5%, we will accrue 41 patients/per Arm to the trial in order to have 39 eligible patients. A total of 55 patients will be enrolled.

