## 1. OBJECTIVES

The paradigm of therapy in Smoldering Multiple Myeloma (SMM) is changing as we develop better therapeutic agents that prevent end organ damage and improve survival of patients with multiple myeloma (MM). Indeed, recent studies of a phase III trial of lenalidomide and dexamethasone versus placebo showed improved response, progression free survival and overall survival in patients with high risk smoldering MM compared to placebo control. Therefore, there is a need to examine novel therapeutic combinations in patients with high risk smoldering MM. Based on the activity of lenalidomide and dexamethasone in patients with high risk SMM and based on the safety and activity profile of elotuzumab and lenalidomide in patients with relapsed MM, we propose to examine the activity of elotuzumab and lenalidomide in patients with high risk SMM.

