## 2.6 Treatment of high risk SMM

In a randomized open-label phase 3 trial, 119 patients with high-risk smoldering myeloma were randomized to treatment or observation. Patients in the treatment group received an induction regimen (lenalidomide at a dose of 25 mg per day on days 1 to 21, plus dexamethasone at a dose of 20 mg per day on days 1 to 4 and days 12 to 15, at 4-week intervals for nine cycles), followed by a maintenance regimen (lenalidomide at a dose of 10 mg per day on days 1 to 21 of each 28-day cycle for 2 years). The primary end point was time to progression to symptomatic disease. Secondary end points were response rate, overall survival, and safety. After a median follow-up of 40 months, the median time to progression was significantly longer in the treatment group than in the observation group (median not reached vs. 21 months; hazard ratio for progression, 0.18; 95% confidence interval [CI], 0.09 to 0.32; P<0.001). The 3-year survival rate was also higher in the treatment group (94% vs. 80%; hazard ratio for death, 0.31; 95% CI, 0.10 to 0.91; P=0.03). A partial response or better was achieved in 79% of patients in the treatment group after the induction phase and in 90% during the maintenance phase. Toxic effects were mainly grade 2 or lower. Early treatment for patients with high-risk smoldering myeloma delays progression to active disease and increases overall survival. (NCT00480363).

CONFIDENTIAL

This document is confidential. Do not disclose or use except as authorized.

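### The 24-of-39 rule compares a regimen containing lenalidomide-dexamethasone with untreated natural history, so a go is nearly certain even if elotuzumab adds nothing

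*Combined protocol and SAP*

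**What the plan says.** Section 13.1 says that the 2-year proportion "will be compared to the rate published for the high risk SMM". It gives the source as the Mayo Clinic model, in which "the median time to progression for patients with high risk SMM was only 1.9 years", and assumes on that basis that "a 2-years progression-free rate of 50% will not be considered promising", whereas "a true progression free rate of 70% or higher will be considered promising". The design is stated as follows: "A single-stage design will be employed with 39 eligible patients entered". With 24 or more progression free at 2 years, "we will conclude that this treatment warrants further study". Stated operating characteristics are 0.10 at a true rate of 50% and above 0.9 at 70%.

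Under Section 5.1 all patients receive elotuzumab, lenalidomide and dexamethasone; there is no doublet-only arm. Section 2.6 describes a randomized phase 3 trial of lenalidomide-dexamethasone against observation in high-risk SMM. Its primary endpoint was time to progression to symptomatic disease, with the treated median not reached against 21 months, and "hazard ratio for progression, 0.18; 95% confidence interval [CI], 0.09 to 0.32". Section 1 uses that activity as the ground for the present trial: "there is a need to examine novel therapeutic combinations in patients with high risk smoldering MM". Section 13 contains no reference rate for the doublet.

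**The concern.** The null and the target both describe what the regimen must beat if the alternative is no treatment. Two of its three drugs already have a randomized result against observation in this disease, and the protocol itself reports it. If the doublet alone would leave well over 70% of patients progression free at 2 years, then both the pass mark (62%) and the promising rate (70%) lie below what the backbone is expected to deliver. A go would then repeat, without a control, a finding that Section 2.6 already gives for the doublet, while the wording in 13.1 reads as support for taking the elotuzumab combination forward. The rule could also pass a result that looks worse than the doublet.

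**Working it through.** **Inputs.** From 13.1: n = 39, cut-off 24, null 50%, target 70%. From 2.6: observation median 21 months, hazard ratio 0.18 (95% CI 0.09 to 0.32), 3-year survival 94% on the doublet. The documents do not give a 2-year progression-free rate for the doublet, so it is derived under assumptions.

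**1. The plan's own figures.** Exact binomial, X ~ Bin(39, p):
- P(X ≥ 24 | p = 0.50) = 0.0998, stated as 0.10.
- P(X ≥ 24 | p = 0.70) = 0.906, stated as above 0.9.

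Both reproduce.

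**2. Implied 2-year rate on the doublet.** Assume exponential times in the observation group and proportional hazards:
- Observation: 0.5^(24/21) = 0.453.
- Doublet: 0.453^HR.

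**3. Probability of a go if elotuzumab adds nothing.**

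| HR | 2-year rate on doublet | P(X ≥ 24 of 39) |
|---|---|---|
| 0.09 | 93.1% | above 0.9999 |
| 0.18 | 86.7% | 0.99998 |
| 0.32 | 77.6% | 0.993 |

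**4. Passing results that look worse than the doublet.** Exact (Clopper-Pearson) 90% upper limits:

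| Progression free, of 39 | 24 | 25 | 26 | 27 | 28 | 29 | 30 |
|---|---|---|---|---|---|---|---|
| Upper limit | 74.6% | 76.8% | 79.0% | 81.2% | 83.3% | 85.4% | 87.4% |

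Results of 24 to 29 pass the rule with an interval wholly below 86.7%. Results of 24 and 25 lie wholly below even 77.6%.

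**5. Sensitivity to other failures.**
- Deaths: suppose the 6% who died within 3 years on the doublet (100% − 94%) all died by year 2 and were additional failures. The rates become 0.867 × 0.94 = 81.5% and 0.776 × 0.94 = 73.0%, with P(go) 0.999 and 0.959.
- Non-evaluable patients counted as failures:

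| Share non-evaluable (assumed) | P(go), HR 0.18 | P(go), HR 0.32 |
|---|---|---|
| 10% | 0.994 | 0.902 |
| 20% | 0.890 | 0.598 |

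- Biochemical progression counted as failure: P(go) falls by an amount that the documents do not allow to be calculated.

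**The case against.** The strongest reply is that the rule does what the protocol says. The primary objective in 1.2 concerns the three-drug combination, Section 1 frames the aim as early intervention in patients with 50% progression at 2 years, and 13.1 names its comparator openly. A reader might infer that the trial claims to isolate elotuzumab's contribution and fails to do so. No section makes that claim, so this is not an error in the design's own terms. What remains is a limit on what a go can support.

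The 87% is also a derived figure. It rests on one median and one hazard ratio, and its range ignores uncertainty in the 21 months. The cited regimen differs in dexamethasone schedule and maintenance lenalidomide dose. Its endpoint was symptomatic progression, whereas this protocol is not uniform: 11.1 refers to symptomatic disease, 11.2.4 includes biochemical progression, 11.2.8 calls PFS the primary endpoint, and 13.1.1 analyses TTP. These points stand as limits on the figure.

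The broader eligibility in 3.1.2 does not help the rule. For a cohort made up only of patients with two Mayo factors (median 5.1 years, Table 1), the exponential untreated 2-year rate is 0.5^(2/5.1) = 76.2%, and P(go) is 0.987 with no treatment at all.

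Finally, 13.1.1 already requires a 2-year estimate with a 90% interval, which a reader could set beside Section 2.6. That is so, but nothing obliges the report to do it.

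**Conclusion.** The point holds as a limit on the conclusion drawn from the rule. On the protocol's own background figures, the doublet alone would give about 87% progression-free at 2 years (78% to 93%), above both the 62% pass mark and the 70% target. A go is then nearly certain with an inert elotuzumab: 0.99998, or 0.993 at HR 0.32. This assumes exponential times, proportional hazards, a comparable regimen and population, and symptomatic progression as the endpoint.

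Two stronger readings are not supported. One is that the rule cannot fail if elotuzumab is inert: with 20% of patients non-evaluable and counted as failures, P(go) is 0.890 at HR 0.18 and 0.598 at HR 0.32. The other is that the pass mark should rise to 30 of 39, the first count whose upper limit reaches 86.7%. That bar has three faults:
- It lowers the probability of a go at the stated 70% target from 0.906 to 0.224.
- It still passes an inert elotuzumab with probability 0.972 at a true rate of 86.7%.
- By the same criterion the bar moves from 26 of 39 (reference 77.6%) to 34 of 39 (reference 93.1%), so 30 is falsely precise.

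**What to change.** In 13.1, keep 24 of 39 with its stated error rates. Add that a go means only that the three-drug regimen exceeds the untreated natural-history rate assumed there, and that it does not show added value of elotuzumab over lenalidomide-dexamethasone.

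In 13.1.1, pre-specify that the Kaplan-Meier 2-year rate and 90% confidence interval, on the symptomatic-progression endpoint, be reported beside the doublet reference from Section 2.6 (about 87%, range 78% to 93%), with the derivation and assumptions shown. Require any recommendation for further study of the combination to state where the interval lies relative to that range. The comparison is descriptive, with no fixed second cut-off.

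The cost is wording in two sections and one extra reported comparison; no patients or procedures are added. The downside is a more cautious conclusion and reliance on a derived external reference.

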## **4. REGISTRATION PROCEDURES**

### **4.1 General Guidelines for DF/HCC and DF/PCC Institutions**

Institutions will register eligible participants in the Clinical Trials Management System (CTMS) OnCore. Registrations must occur prior to the initiation of protocol therapy. Any participant not registered to the protocol before protocol therapy begins will be considered ineligible and registration will be denied.

An investigator will confirm eligibility criteria and a member of the study team will complete the protocol-specific eligibility checklist.

Following registration, participants may begin protocol therapy. Issues that would cause treatment delays should be discussed with the Overall Principal Investigator (PI). If a participant does not receive protocol therapy following registration, the participant's registration on the study must be canceled. Registration cancellations must be made in OnCore as soon as possible

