### 5. TREATMENT PLAN

#### 5.1 Treatment Regimen

All patients will be treated with elotuzumab, lenalidomide and dexamethasone. Patients will also be stratified by age >65 years or older and high risk cytogenetics based on t(4:14), t(14:16), 17p deletion or p53 mutation, +1q amplification.

A treatment cycle is defined as 28 consecutive days.

CONFIDENTIAL

This document is confidential. Do not disclose or use except as authorized.

Elotuzumab will be administered Cycles 1 and 2 on days 1, 8, 15, 22 and cycles 3-8 on days 1 and 15. Lenalidomide will be administered days 1-21 every 28 days. Dexamethasone will be administered on days 1, 8, 15 and 22 on cycles 1-2 then on days 1, 8 and 15 on cycles 3-8. Patients on maintenance treatment will be administered elotuzumab on day 1, and lenalidomide on days 1-21. For treatment cycles 1 and 2, a +/- 3 day window is allowed.

For treatment cycle 3-24, a +/- 7 day window is allowed. Treatment will be administered on an *outpatient* basis.

Reported adverse events and potential risks are described in Section 7. Appropriate dose modifications are described in Section 6. No investigational or commercial agents or therapies other than those described below may be administered with the intent to treat the participant's malignancy.

The participant will be requested to maintain a medication diary of each dose of lenalidomide and dexamethasone. The medication diary should be returned to clinic staff at the end of each cycle.

Elotuzumab and Lenalidomide Dexamethasone Combination (Cycles 1-2)					
Agent	Premedication and Precautions	Schedule	Dose	Route	Cycle Length
Elotuzumab	Premedications are described below	Days 1, 8, 15, 22	10 mg/kg	Intravenous-See appendix B for more details	28 days (4 weeks)
Lenalidomide	None	Days 1-21 of each cycle	25 mg	Oral	
Dexamethasone	Take with food; recommended to be taken in the morning	Days 1, 8, 15, 22	8 mg	IV	
			32 mg	Oral	

CONFIDENTIAL

This document is confidential. Do not disclose or use except as authorized.

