### 13.1.1 Analysis of Primary Endpoint

Time to progression (TTP) is defined as the time from protocol therapy initiation until documented progression, censored at date last known progression-free for those who have not progressed. At time of final analysis, the 2-year progression-free rate will be estimated using the Kaplan-Meier method with 90% confidence interval per Arm. All patients who have received one dose of study treatment will be included for the TTP analysis, including those who die or are lost to follow-up within 2 years.

The percent of patients who undergo stem cell mobilization and the modality of mobilization will be noted in the study. These patients will not be censored.

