### **13.2 Sample Size, Accrual Rate and Study Duration**

A total of 55 patients will be enrolled. We expect 3.5 years of active accrual (approximately 2 patients per month) and 3 years of follow-up of patients.

The final analyses of progression-based endpoints, such as estimating the 2-year progression-free rate and estimating the TTP distribution, will be conducted at the end of the study, which will occur after either all subjects have progressed or died or 2-years after the initiation of therapy of the last subject enrolled, whichever occurs first.

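### The go/no-go rule is set for 39 eligible patients, but the trial enrols 55 and analyses all dosed patients by Kaplan-Meier, so the plan does not say which patients or which result decide

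*Combined protocol and SAP*

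**What the plan says.** Section 13.1 takes a 2-year progression-free rate of 50% as not promising and 70% as promising, and uses a single-stage design with 39 eligible patients. The rule reads: "If 24 or more of the 39 eligible patients are progression free at 2 years (observed rate of 62" per cent), the treatment warrants further study. Its operating characteristics follow: "The probability of concluding that the treatment is effective if the true rate is 50% is 0.10 and is >0.9" at 70%. The paragraph then allows for 5% ineligibility and ends: "we will accrue 41 patients/per Arm to the trial in order to have 39 eligible patients. A total of 55 patients will be enrolled". Section 13.2 repeats the total of 55. Section 13.1.2 still computes its confidence-interval width on 39 eligible patients.

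Section 13.1.1 describes the primary analysis in other terms. The estimator: "the 2-year progression-free rate will be estimated using the Kaplan-Meier method with 90% confidence interval per Arm". The set: "All patients who have received one dose of study treatment will be included for the TTP analysis", explicitly including patients who die or are lost within 2 years. Neither the estimate nor its interval is compared with 50%, 62% or any other value.

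Section 5.1 gives everyone one regimen: "All patients will be treated with elotuzumab, lenalidomide and dexamethasone". Under Section 4.1, if a registered patient is not treated, the "registration on the study must be canceled". The dosed set can therefore be as large as 55.

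**The concern.** The rule and the analysis differ in three respects.

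- **Number:** 39 against 55.
- **Patients:** eligible against dosed.
- **Quantity:** a count of successes against a Kaplan-Meier estimate with censoring.

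The plan does not say which 39 patients the rule would use, what cutoff applies to a larger number, or whether the count or the curve settles the question. This is the plan's only efficacy decision rule. With 55 patients in hand, two analysts following the text in good faith could report opposite conclusions from the same data.

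**Working it through.** **Inputs.** Section 13.1 gives p0 = 0.50, p1 = 0.70, n = 39, cutoff 24 and ineligibility 5%. Sections 13.1 and 13.2 give enrolment of 55.

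**1. The plan's own figures.** With X ~ Binomial(39, p), P(X ≥ 24) is 0.0998 at p = 0.50 and 0.906 at p = 0.70. The plan states 0.10 and above 0.9, so it is right for 39. The neighbouring cutoffs do not fit: 23 gives 0.168/0.950 and 25 gives 0.054/0.836.

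**2. From 39 to 41 to 55.** 39 × 1.05 = 40.95, which rounds to 41, and 41 × 0.95 = 38.95, so 41 is consistent with 39. The 55 is not: 55 × 0.95 = 52.25, or about 52 eligible. Having only 39 eligible among 55 would need 1 − 39/55 = 29% ineligible.

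**3. Candidate rules for the larger trial.** These are exact binomial and assume every patient's 2-year status is known.

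| Rule | Proportion | Alpha (50%) | Power (70%) |
|---|---|---|---|
| 24 of first 39 | 61.5% | 0.0998 | 0.906 |
| 32 of 52 | 61.5% | 0.063 | 0.928 |
| 33 of 55 | 60.0% | 0.089 | 0.958 |
| 34 of 55 | 61.8% | 0.052 | 0.927 |
| 35 of 55 | 63.6% | 0.029 | 0.879 |

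Since 24/39 × 55 = 33.8, 34 of 55 carries the plan's proportion over. For 55 patients, 33 is the smallest cutoff with alpha at or below 0.10 (32 gives 0.140).

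**4. How often the readings conflict.** Let X be successes in the first 39 and Y ~ Binomial(16, p) successes in the remaining 16. The two readings disagree when exactly one of X ≥ 24 and X + Y ≥ 34 holds. Summing over all (X, Y):

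- p = 0.50: 7.2% (6.0% pass on the first 39 only, 1.2% pass on 34 of 55 only)
- p = 0.60: 18.0%
- p = 0.70: 6.9%

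Against 32 of 52 the figures are 6.7%, 16.3% and 6.3%.

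**5. Choosing after the fact.** If success on either reading counts, alpha is 0.0998 + 0.0123 = 0.112 for the first 39 with 34 of 55. It is 0.115 with 32 of 52, and 0.131 with 33 of 55.

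**6. If the Kaplan-Meier estimate decides.** This was simulated by comparing the 2-year estimate with the cutoff proportion. The assumptions are exponential progression and 5% or 10% independent censoring before 2 years, spread evenly, early or late. None of these comes from the plan.

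- 33 of 55: alpha 0.06–0.08, power 0.935–0.943
- 34 of 55: alpha 0.036–0.047, power 0.892–0.904
- 32 of 52: alpha 0.044–0.056, power 0.894–0.903

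**7. If patients lost early count as failures.** The success probability at the alternative becomes 0.70 × 0.95 or 0.70 × 0.90. Power at 5% and 10% loss is then 0.797 and 0.643 for 24 of 39, 0.877 and 0.728 for 33 of 55, and 0.818 and 0.645 for 32 of 52.

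**The case against.** The literal text can be read coherently. A 39-patient set decides, and the Kaplan-Meier estimate with its interval reports the result. An estimate need not carry its own threshold, and Section 13.1.2 also still refers to 39 eligible patients. The stakes are bounded too. The rule decides only whether further study is warranted, alpha moves to 0.112 when a reading is chosen afterwards, and the largest disagreement falls at 60%, where the design calls neither conclusion wrong. All of this stands, and it limits the weight of the point. It does not supply the missing statement of which 39 patients count and which result decides.

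It might also be said that the printed 62% is the threshold. It is 24/39 rounded. Taken literally on 55 patients it requires 35, with power 0.879, which is below the plan's own claim.

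Stronger readings are tempting, but the documents do not support them.

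- A reader might infer that 24 successes suffice among 55. That would pass with probability 0.86 at a true rate of 50%. But Section 13.1 ties the 24 to 39 patients, so this shows only that the count cannot be carried over unchanged.
- A reader might infer from the references to arms that 55 is the remnant of a multi-arm design. Section 5.1 describes one regimen and no text says this. The schema page is not in the text available for review.

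**Conclusion.** The plan is internally inconsistent as written and should be corrected. The arithmetic of the 24-of-39 rule is right; the defect is that the rule does not fit the trial as sized and analysed. The size is about 7% opposite conclusions at either design value and 18% midway, for the first 39 against 34 of 55, with alpha of 0.112 if either reading may be claimed.

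The finding should not be read as lost power or uncontrolled error. Each candidate in the table keeps alpha at or below 0.10, and 34 of 55, 33 of 55 and 32 of 52 all have more power than 24 of 39 when follow-up is complete.

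The exact figures assume independent patients from one group with known 2-year status. The 52 is an inference from the 5% allowance. The Kaplan-Meier figures depend on the assumed censoring and do not model deaths. That gap is real: Section 13.1.1 bases the primary analysis on time to progression, while Section 11.2.8 names progression-free survival, which counts deaths, as the primary endpoint. A patient who dies without progression therefore has no settled outcome under either the count or the curve.

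**What to change.** 1. Explain 55 against 41, and confirm that the 55 are one group.
2. Name one decision set and one cutoff. The default is 24 of the first 39 eligible patients by registration order, with the Kaplan-Meier estimate in all dosed patients as supportive; this keeps 0.0998/0.906. The alternative is to restate the cutoff for the full set with its exact error rates, but only if it is documented as fixed without sight of 2-year outcomes. In that case 34 of 55 keeps the plan's proportion (0.052/0.927). 33 of 55 (0.089/0.958) lowers the bar to 60%, which is harder to defend late in an open-label trial. If the set is eligible patients and numbers 52, 32 of 52 gives 0.063/0.928.
3. State whether the count or the Kaplan-Meier estimate decides, and how deaths without progression and patients lost before 2 years are counted. Say that the binomial figures hold only with complete 2-year status. If the Kaplan-Meier estimate decides with 5–10% censoring, do not claim power above 0.9 for 34 of 55 or 32 of 52.

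The cost is a wording amendment and no extra patients. The default gives up the additional patients for the decision; the alternative requires a record that outcomes were unseen.

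As a separate minor clean-up, reconcile the references to arms (13.1, 13.1.1, 13.1.2), cohorts (13.5) and randomization (11.2.7, 11.2.8) with the single regimen. The accrual line in 13.2 also needs correcting: 2 per month × 42 months = 84, not 55.
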